16.3.1. LABORATORY SPECIFIC DERIVATIONS

- Log ALT = logarithm to base 10 scale of the multiple of the ULN of ALT
- Log AST = logarithm to base 10 scale of the multiple of the ULN of AST
- Log TBL = logarithm to base 10 scale of the multiple of the ULN of TBL. Note: Bilirubin value instead of TBL will be used.
- Potential Hy's law categories:
 - Category 1: ALT or AST $\geq 3 \times \text{ULN}$ and TBL $\geq 2 \times \text{ULN}$ within the same sample
 - Category 2: TBL $\geq 2 \times \text{ULN}$ within 30 days after transaminase peak (ALT or AST $\geq 3 \times \text{ULN}$)
- Potential Hy's Law subjects are defined as subjects with laboratory data in at least one Potential Hy's law categories at any time point of the trial.
- Drug induced liver injury (DILI):

1. Normal liver function at Baseline is defined as AST and ALT and Total Bilirubin values measured

Document: \\eedc-nas01a:\Boehringer_Ingelheim\BI_695501\XXA39605\Biostatistics\Documentation\SAP\15-v2.0\BI 1297.12 SAP v2.0 31JAN2018.docx

Author:

Version Number:

2.0

Version Date:

31JAN2018

Template No: CS_TP_BS016 Revision 4

Reference: CS_WI_BS005

Effective Date: 01Apr2016

Copyright © 2009, 2010, 2012, 2016

All rights reserved.

The contents of this document are confidential and proprietary to reproduction is strictly prohibited.

Unauthorized use, disclosure or

- at baseline are each \leq respective ULN.
2. Impaired liver function tests at Baseline is defined as AST or ALT or Total Bilirubin values measured at baseline is $>$ respective ULN.
 3. For post baseline visits:
 1. Category 1: Subject with normal liver function at Baseline and (AST and/or ALT ≥ 3 times ULN and TBL ≥ 2 times ULN within the same sample).
 2. Category 2: Subject with impaired liver function at Baseline and (AST and/or ALT ≥ 3 times the Baseline value and TBL ≥ 2 times the Baseline value within the same sample.).
 3. Category 3: marked peak aminotransferase (ALT, and/or AST) elevations ≥ 10 fold ULN

16.3.2. LABORATORY REFERENCE RANGES AND ABNORMAL CRITERIA

Quantitative laboratory measurements will be compared with the relevant laboratory reference ranges in SI units and categorized as:

- Low: Strictly below the lower limit of the laboratory reference range.
- Normal: Within the laboratory reference range (upper and lower limit included).
- High: Strictly above the upper limit of the laboratory reference range.

16.3.3. OTHER SAFETY LABORATORY EVALUATIONS

16.3.3.1. Pregnancy test

Descriptive table will present pregnancy results for females by visit on SAF.

The pregnancy results will be listed as well.

16.3.3.2. Tuberculosis test

Descriptive table will present Tuberculosis (TB) test results by visit on SAF.

The TB test results will be listed as well.

16.4. ECG EVALUATIONS

Results from ECGs will be summarized by visit to the categories as recorded in the eCRF page "12-Lead-ECG" ("Normal", "Abnormal, not clinically significant" and "Abnormal, clinically significant").

Document: \\ieedc-nas01a:\Boehringer_Ingelheim\BI_695501\XXA39605\Biostatistics\Documentation\SAP\15-v2.0\BI 1297.12 SAP v2.0 31JAN2018.docx

Author:

Version Number:

2.0

Version Date:

31JAN2018

Template No: CS_TP_BS016 Revision 4

Reference: CS_WI_BS005

Effective Date: 01Apr2016

Copyright © 2009, 2010, 2012, 2016

All rights reserved.

The contents of this document are confidential and proprietary to reproduction is strictly prohibited.

Unauthorized use, disclosure or

ECG evaluations will also be listed.

16.5. VITAL SIGNS

The following Vital Signs measurements will be reported:

- Sitting Systolic Blood Pressure (mmHg)
- Sitting Diastolic Blood Pressure (mmHg)
- Sitting Pulse Rate (bpm)
- Temperature (°C). Conversion: $\text{Temperature}(\text{°C}) = [\text{Temperature}(\text{F}) - 32] / 1.8$

Weight will be presented along with vital signs.

- Weight (kg)

The handling of retests, unscheduled, and end of trial measurements is described in Section 6.3.

The summary of actual and change from baseline by visit will be provided for vital sign data. In case of multiple measurement timepoints at one visit, the pre-injection data will be used for summary tables.

Vital signs data will be listed.

16.6. PHYSICAL EXAMINATION

Incidence of evaluation categories (Normal, Abnormal) at baseline and post-baseline visits will be provided for physical examination data.

The handling of retests, unscheduled, and end of trial measurements is described in Section 6.3.

Baseline is described in Section 6.2.

Document: \\ieedc-nas01a:\Boehringer_Ingelheim\BI_695501\XXA39605\Biostatistics\Documentation\SAP\15
-v2.0\BI 1297.12 SAP v2.0 31JAN2018.docx

Author:

Version Number:

2.0

Version Date:

31JAN2018

Template No: CS_TP_BS016 Revision 4

Reference: CS_WI_BS005

Effective Date: 01Apr2016

Copyright © 2009, 2010, 2012, 2016

All rights reserved.

The contents of this document are confidential and proprietary to
reproduction is strictly prohibited.

Unauthorized use, disclosure or

Document: \\eedc-nas01a:\Boehringer_Ingelheim\BI_695501\XXA39605\Biostatistics\Documentation\SAP\15
-v2.0\BI 1297.12 SAP v2.0 31JAN2018.docx

Author: Version Number: 2.0
Version Date: 31JAN2018

Template No: CS_TP_BS016 Revision 4
Effective Date: 01Apr2016

Reference: CS_WI_BS005

Document: \\eedc-nas01a:\Boehringer_Ingelheim\BI_695501\XXA39605\Biostatistics\Documentation\SAP\15
-v2.0\BI 1297.12 SAP v2.0 31JAN2018.docx

Author:

Version Number:

2.0

Version Date:

31JAN2018

Template No: CS_TP_BS016 Revision 4
Effective Date: 01Apr2016

Reference: CS_WI_BS005

Copyright © 2009, 2010, 2012, 2016

All rights reserved.

The contents of this document are confidential and proprietary to
reproduction is strictly prohibited.

Unauthorized use, disclosure or

Document: \\eedc-nas01a:\Boehringer_Ingelheim\BI_695501\XXA39605\Biostatistics\Documentation\SAP\15
-v2.0\BI 1297.12 SAP v2.0 31JAN2018.docx

Author: Version Number: 2.0
Version Date: 31JAN2018

Template No: CS_TP_BS016 Revision 4
Effective Date: 01Apr2016

Reference: CS_WI_BS005

Document: \\eedc-nas01a:\Boehringer_Ingelheim\BI_695501\XXA39605\Biostatistics\Documentation\SAP\15
-v2.0\BI 1297.12 SAP v2.0 31JAN2018.docx

Author: Version Number: 2.0
Version Date: 31JAN2018

Template No: CS_TP_BS016 Revision 4
Effective Date: 01Apr2016

Reference: CS_WI_BS005

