5.3.1 Physical examination

A physical examination will be performed at the visits indicated in the [Flow Chart](#).

The physical examination will include assessment of general appearance, skin, head, neck, throat, lymph nodes, cardiovascular and neurological systems, thyroid gland, musculoskeletal system/limbs, respiratory tract and abdomen.

Clinically relevant abnormal findings will be reported as Baseline conditions or AEs.

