5.3.4 Electrocardiogram

The 12-lead ECGs will be performed as scheduled in the [Flow Chart](#).

ECGs will be recorded after the patients have rested for at least 5 minutes in a supine position and will always precede blood sampling.

ECGs may be repeated for quality reasons and the repeat used for analysis. Additional ECGs may be recorded for safety reasons. Clinically relevant, abnormal findings will be reported as AEs.

Information about the details of ECG collection and the parameters assessed will be provided in the ISF.

The original ECG traces and variables must be stored in the patients' medical record as source data. A physician familiar with interpretation of ECG will evaluate the ECG from a clinical perspective and the result (whether the ECG result is normal, abnormal not clinically relevant or abnormal clinically relevant) will be recorded in the appropriate section of the eCRF.

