7.3.4 Safety analyses

Adverse events will be coded using the Medical Dictionary for Drug Regulatory Activities (MedDRA). The analysis of AEs will be based on the concept of treatment-emergent AEs. That means that all AEs with an onset between start of treatment and end of the REP, a period of 10 weeks after the last dose of trial medication, will be assigned to the treatment

period for evaluation. AEs that start before first drug intake and deteriorate under treatment will also be considered as ‘treatment-emergent’. Other AEs will be assigned to the appropriate trial phases, i.e., screening or post-treatment.

All treated patients will be included in the safety analysis. In general, safety analyses will be descriptive in nature and will be based on BI standards. No hypothesis testing is planned.

Statistical analysis and reporting of adverse events will concentrate on treatment-emergent adverse events. To this end, all adverse events occurring between start of treatment and end of the residual effect period will be considered ‘treatment-emergent’. The residual effect period is defined as 10 weeks after last dose of trial medication. Adverse events that start before first drug intake and deteriorate under treatment will also be considered as ‘treatment-emergent’.

Frequency, severity, and causal relationship of adverse events will be tabulated by system organ class and preferred term after coding according to the current version of the Medical Dictionary for Drug Regulatory Activities (MedDRA).

Laboratory data will be analysed both quantitatively as well as qualitatively. The latter will be done via comparison of laboratory data to their reference ranges. Values outside the reference range as well as values defined as clinically relevant will be highlighted in the listings. Treatment groups will be compared descriptively with regard to distribution parameters as well as with regard to frequency and percentage of patients with abnormal values or clinically relevant abnormal values.

Vital signs, physical examinations, or other safety-relevant data observed at screening, baseline, during the course of the trial and at the end-of-trial evaluation will be assessed with regard to possible changes compared to findings before start of treatment.

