6.3. RETESTS, UNSCHEDULED VISITS AND EARLY TERMINATION DATA

In general, for by-visit summaries, data recorded at the nominal visit will be presented. In the case of a retest, an unscheduled assessment will be created. For laboratory assessments as described in APPENDIX 5, the latest available measurement within 2 days after the planned assessment will be used for by-visit summaries. Unless assigned to a planned visit number, unscheduled measurements will not be included in by-visit summaries except for DILIs (refer to section 16.3).

Subjects who are terminated from the study early will have their End of Treatment (EoT) visit on a date which may or may not coincide with the window designated for one of the 8 regular planned visits.

Remapping of EOT visit assessment data to a regular scheduled visit will be performed only if the EOT visit

Document: \\eedc-nas01a:\Boehringer_Ingelheim\BI_695501\XXA39605\Biostatistics\Documentation\SAP\15
-v2.0\BI 1297.12 SAP v2.0 31JAN2018.docx

Author: Version Number: 2.0
Version Date: 31JAN2018

Template No: CS_TP_BS016 Revision 4
Effective Date: 01Apr2016

Reference: CS_WI_BS005

assessment was performed during the window for a regular scheduled visit and if the assessment value is non-missing for each regular planned visit between the last regular planned visit for which it was non-missing and the date of the EOT visit. Otherwise, the data will be classified as Early Termination and identified as such in the relevant listings.

If a subject's EOT visit for an assessment was performed in the window designated for a regular planned visit X and the last time point prior to visit X at which the assessment was to have been performed, according to the study flow chart, is the last regular planned visit for which it was non-missing then the assessment's value will be mapped to visit X, if it is an assessment that is scheduled to be performed at visit X.

If a subject's EOT visit for an assessment was performed at some time point after the window designated for a regular planned visit X and before the window designated for a regular planned visit X + 1 and the last time point prior to visit X + 1 at which the assessment was to have been performed, according to the study flow chart is the last regular planned visit for which it was non-missing then the assessment's value will be mapped to visit X + 1, if it is an assessment that is scheduled to be performed at visit X + 1.

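### Physical examination and ECG are planned only as category counts by visit, which show net change but not the shift from pre-treatment findings that the protocol commits to assessing

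*SAP*

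**What the plan says.** **Commitment.** Protocol 7.3.4 says that vital signs, physical examinations and other safety-relevant data "will be assessed with regard to possible changes compared to findings before start of treatment". Comparing the safety profiles of the two products is a secondary objective (Protocol 2.2, SAP 2.2).

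**Planned output.** SAP 16.6: "Incidence of evaluation categories (Normal, Abnormal) at baseline and post-baseline visits will be provided for physical examination data". SAP 16.4: "Results from ECGs will be summarized by visit to the categories as recorded in the eCRF page". That page has three categories: normal, abnormal but not clinically significant, and abnormal and clinically significant. SAP 16.4 adds "ECG evaluations will also be listed"; SAP 16.6 states no listing. Neither section plans a within-patient comparison with baseline.

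**Other domains in the same SAP.** Laboratory data get shift tables from baseline category (16.3). Vital signs get change from baseline (16.5).

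**Records in the by-visit tables.** SAP 6.3: "Unless assigned to a planned visit number, unscheduled measurements will not be included in by-visit summaries except for DILIs". End-of-treatment assessments of early terminators move to a regular visit only under stated conditions, one being that the assessment is scheduled at that visit. The rest are labelled Early Termination and identified in listings. Protocol 5.3.4 foresees extra recordings: "Additional ECGs may be recorded for safety reasons".

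**The concern.** A count of abnormal results at each visit is a marginal total. One patient who becomes abnormal and one who returns to normal offset each other. Two arms can therefore show the same counts while differing in how many patients developed an abnormality on treatment.

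The protocol's sentence is about change against findings before treatment. The SAP answers it with a change measure or a shift table for vital signs and laboratory data, but not for these two domains. The records most easily lost from the by-visit tables are ECGs taken outside the schedule and some assessments of patients who stop early. At stake is part of the descriptive safety comparison, not the efficacy conclusion.

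**Working it through.** The documents give no abnormality rates and no figure on this point, so there is nothing to reproduce. The check is a bound on what counts by visit can reveal, followed by a reading of SAP 6.3 against the visit schedule.

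**1. What the counts identify**

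Inputs: about 300 patients randomized 1:1 (Protocol 3.1), so N = 150 per arm. The abnormal rates are assumptions. The same patients are taken to be assessed at both times.

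Let a0 be the number abnormal at baseline, a1 the number abnormal later, n the newly abnormal and r the resolved. Then

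a1 = a0 + n − r,

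so the counts fix only n − r. The possible values of n run from max(0, a1 − a0) to min(a1, N − a0).

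| Abnormal at baseline and later (assumed) | a0 = a1 | Lowest n | Highest n |
|---|---|---|---|
| 10% | 15 | max(0, 0) = 0 | min(15, 135) = 15 |
| 20% | 30 | max(0, 0) = 0 | min(30, 120) = 30 |
| 30% | 45 | max(0, 0) = 0 | min(45, 105) = 45 |

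These are logical limits, not expected values. A shift table reports n and r directly.

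**2. Which records drop out**

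- Unscheduled ECG: left out of the by-visit table unless it was assigned to a planned visit number. DILI is the only exception.
- End of treatment: Protocol 6.2.2 places ECG and physical examination in the treatment period at Visits 5, 7 and 9. Take an end-of-treatment ECG done after the Visit 5 window and before the Visit 6 window. SAP 6.3 would map it to Visit 6, but only if ECG is scheduled there, and it is not. The record becomes Early Termination. The same happens between the Visit 7 and Visit 8 windows.
- A record between the Visit 6 and Visit 7 windows can be mapped to Visit 7 if the Visit 5 value is present. The omission is therefore partial.

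**3. What the AE tables recover**

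Clinically relevant ECG or physical-examination findings are recorded as AEs, or as baseline conditions if already present (Protocol 5.3.1, 5.3.4, 5.3.6.2). TEAEs are tabulated by SOC and PT (SAP 16.1.2). A patient who moves from normal to abnormal but not clinically significant on ECG does not have to enter that route. No planned table counts that move by arm.

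**The case against.** The strongest reply has four parts.

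- **The protocol prescribes no shift table.** SAP 16.6 shows categories at baseline and afterwards, which is a comparison with pre-treatment findings, and randomized arms can be compared on post-baseline proportions. This stands in part: net change is visible. ECG is covered only as other safety-relevant data, and SAP 16.4 does not mention baseline. Net counts still do not show change within patients.
- **Clinically relevant findings reach the AE tables.** This stands. A reader might infer that new abnormalities cannot be compared between arms at all. The documents do not support that, because clinically relevant ones are compared in the TEAE tables.
- **Safety-triggered ECGs are not lost.** This stands. A reader might infer that they vanish from the report. The exclusion concerns by-visit summaries only and does not apply to a record assigned to a planned visit. SAP 6.3 puts unscheduled data in the listings, and ECGs are listed. A listing does not, however, give an arm comparison.
- **The size of the loss is unknown.** This also stands. An example in which new and resolved abnormalities cancel exactly shows what is possible, not what is likely.

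A further tempting inference concerns skin. Protocol 5.3.1 says "The physical examination will include assessment of general appearance, skin, head, neck, throat", and every patient enters with at least 10% BSA involved. A reader might conclude that the physical-examination table starts near 100% abnormal, so that nothing new can register. That holds only if one overall result is tabulated and known psoriasis is scored abnormal: then a0 = N and the upper limit for n is min(a1, 0) = 0. The documents say neither, and the table templates mentioned in SAP 8, which might settle it, are not part of the text available.

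**Conclusion.** The gap is real but small. For physical examination and ECG, the SAP does not deliver the within-patient comparison that fits the commitment in Protocol 7.3.4 and that it already delivers for laboratory data and vital signs. What is missing is the shift itself, the arm comparison of new abnormalities not reported as AEs, and the summary by arm of the unscheduled and end-of-treatment records that SAP 6.3 leaves out.

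The range of 0 to 30 newly abnormal patients per arm rests on an assumed 20% abnormal rate at both times and complete data in 150 patients. It shows that the counts are uninformative about n; it does not estimate a difference between arms. The skin issue remains a question for the eCRF and the table templates. All of this output is descriptive, so the point is an inexpensive improvement and not a defect that threatens the trial's conclusion.

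**What to change.** Add to SAP 16.4 and 16.6 one descriptive shift table each, by arm on the SAF, from baseline to worst post-baseline category, with unscheduled and Early Termination records included.

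- **ECG:** the three eCRF categories. Use the baseline definition in SAP 6.2; the Flow Chart schedules the pre-treatment ECG at Screening.
- **Physical examination:** Normal/Abnormal, by body system with skin shown separately if the eCRF records it that way. If it does not, state how known psoriasis is scored.

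The data are already collected, and the SAP already uses a shift format for laboratory data. The cost is SAP wording and two tables. One drawback is that a worst category depends partly on how many extra assessments a patient had. A footnote giving the number of assessments by arm, or a companion shift table restricted to scheduled visits, deals with that.

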APPENDIX 1. PROGRAMMING CONVENTIONS FOR OUTPUTS

Output Conventions

File names should only consist of lowercase letters, digits (0 to 9) and hyphens. A period should only be used to indicate a separator between the file name and the extension. No spaces, other special characters or punctuation marks are permitted.

The program, program log and output file name should reflect the type of the statistical output. The output files will contain the output number in addition. If this is not possible, then the output name should be at least as descriptive as possible. A prefix can be used to distinguish between a Table, Listing and Figure document ('t' for table, 'l' for listing and 'f' for figure). If there is only 1 digit in the number of the table, listing or figure in the place where 2 digits are possible, a leading zero should be added in the file name to make sorting consistent with the sequence (eg t-14-3-01-1.RTF)

As far as possible, output files should be in RTF format.

The outputs will be provided in pdf format.

Paper Size, Orientation and Margins

The size of paper will be Letter.

The page orientation should preferably be landscape, but portrait is also permitted.

Margins should provide at least 1 inch (2.54 centimeters) of white space all around the page, regardless of the paper size.

The number of columns per page (linesize) should 134 for Letter.

The number of rows per page (pagesize) should be 40 for Letter.

FONTS

The font type 'Courier New' should be used as a default for tables and listings, with a font size of 8. The font color should be black. No bolding, underlining italics or subscripting should be permitted. Try to avoid using superscripts, unless absolutely necessary. Single spacing should be used for all text.

Figures should have a default font of "Times Roman", "Helvetica", or "Courier New".

This can be achieved by using the following options in SAS:

```
goptions  
gunit = pct  
cback = white  
colors = (black)  
hby = 2.4
```

Document: \\ieedc-nas01a:\Boehringer_Ingelheim\BI_695501\XXA39605\Biostatistics\Documentation\SAP\15
-v2.0\BI 1297.12 SAP v2.0 31JAN2018.docx

Author: Version Number: 2.0
Version Date: 31JAN2018

Template No: CS_TP_BS016 Revision 4
Effective Date: 01Apr2016

Reference: CS_WI_BS005

ftext = "TimesRoman"
htext = 2.5;

HEADER INFORMATION

Headers should be defined as follows:

- The header should be placed at the top of the page (same place on each page) regardless of the size or orientation of the table or listing
- The customer name and protocol number should appear in row 1, left-aligned
- The output identification number should appear in row 2, left-aligned
- The output title should start in row 2 after output identification number separated by a double dot, left-aligned
- The output population should appear in row 2 after output title separated by a dash, left-aligned. The population should not be spelled out in full, e.g. FAS in preference to Full analysis set.
- Row 3 should be a continuous row of underscores ('_') (the number of underscores should equal the linesize)
- Row 4 should be a blank line
- Mixed case should be used for titles
- The output titles should be designed so that they are arranged consistently through all outputs. For example, content (e.g., Vital Signs) followed by metric (e.g., Change from Baseline) e.g. Vital Signs – Change from Baseline.
- Titles should not contain quotation marks or footnote references
- The column headings should be underlined with a row of underscores ('_')
- Column headings spanning more than one column should be underlined and have underscores on either side of the title and should be centered
- Column headings containing numbers should be centered
- Column headings should be in sentence case
- In general, the population count should appear in the column header in the form "(N=XXX)"
- "Statistic" should be the column header over n, Mean, SE, n (%) etc.
- As a rule, all columns should have column headings.

TABLE AND LISTING OUTPUT CONVENTIONS

General:

- The first row in the body of the table or listing should be blank
- The left hand column should start in column 1. No indenting or centering of the output should occur.

Document: \\ieedc-nas01a:\Boehringer_Ingelheim\BI_695501\XXA39605\Biostatistics\Documentation\SAP\15-v2.0\BI 1297.12 SAP v2.0 31JAN2018.docx

Author: Version Number: 2.0
Version Date: 31JAN2018

Template No: CS_TP_BS016 Revision 4
Effective Date: 01Apr2016

Reference: CS_WI_BS005

- Rounding should be done with the SAS function ROUND, if no further specification.
- Numbers in tables should be rounded, not truncated, if no further specification.
- Alphanumeric output should be left aligned.
- Numbers should be decimal point aligned.
- Whole numbers should be right aligned.
- Text values should be left aligned.
- The first letter of a text entry should be capitalized
- Listings of adverse events, concomitant medications, medical histories etc. should be sorted in chronological order, with earliest adverse event, medication or history coming first.
- The trial drug should appear first in tables with treatments as columns
- In general, only present totals (across treatment groups) at baseline/randomization, and do not present them post randomization.
- If possible, include 100% frequencies in the table shell, so that it is clear what the denominator is for percentage calculations.
- All listing outputs should be sorted (preferably by Treatment, Site Number and Subject Number).
- Do not use superscripts and subscripts
- The width of the entire output should match the linesize option

Univariate Statistics:

- Statistics should be presented in the same order across tables (i.e., n, Mean, SD, Median, IQR, Minimum, Maximum or n, gMean, gCV, Mean, CV, SD, Median, Minimum, Maximum)
- Table statistics should line up under the N part of the (N=XXX) in the table header. All decimal points should line up. If the minimum and maximum are output on one line as Minimum, Maximum then the comma should line up with the decimal point.
- If the original data has N decimal places, then the summary statistics should have the following decimal places:
 - Minimum and maximum: N
 - Mean, gMean, median, gCV% and CV%: N + 1
 - SD, IQR: N + 2

Frequencies and percentages (n and %):

- Percent values should be reported inside parentheses, with one space between the count and the left parenthesis of the percentage. Parentheses should be justified to accept a maximum of 100.0 as a value and padded with blank space if the percent is less than 100.0. An example is given below:

77 (100.0%)
50 (64.9%)
0 (0.0%)

- Percentages will be reported to one decimal place, except percents <100.0% but >99.9% will be presented as '>99.9%' (e.g., 99.99% is presented as >99.9%); and percents < 0.1%

Document: \\eedc-nas01a:\Boehringer_Ingelheim\BI_695501\XXA39605\Biostatistics\Documentation\SAP\15
-v2.0\BI 1297.12 SAP v2.0 31JAN2018.docx

Author:

Version Number:

2.0

Version Date:

31JAN2018

Template No: CS_TP_BS016 Revision 4

Reference: CS_WI_BS005

Effective Date: 01Apr2016

Statistical Analysis Plan

will be presented as '<0.1%' (e.g., 0.08% is presented as <0.1%). Rounding will be applied after the <0.1% and >99.9% rule.

E.g., (<0.1%)
(6.8%)
(>99.9%)

- Percentages may be reported to 0 decimal places as appropriate (for example, where the denominator is relatively small).
- Where counts are zero, percentages of 0.0% should appear in the output.

Confidence Intervals:

- As a rule confidence intervals are output to one place more than the raw data, and standard deviations and standard errors to two places more than the raw data
- Confidence intervals should be justified so that parentheses displayed on consecutive lines of a table "line up".
- Boundary values of confidence intervals should be separated by a comma.
- Boundary values should be padded as necessary to accept negative values and to allow alignment of the decimal place.
- An example is given below:

(-0.12, -0.10)
(9.54, 12.91)

P-values:

- P-values should be reported to three decimal places, except values <1.000 but >0.999 will be presented as '>0.999' (e.g., 0.9998 is presented as >0.999); and values <0.001 will be presented as '<0.001' (e.g., 0.0009 is presented as <0.001). Rounding will be applied after the <0.001 and >0.999 rule

Ratios:

- Ratios should be reported to one more decimal place than the original data.

Spacing:

- There must be a minimum of 1 blank space between columns (preferably 2)

Denominators:

- If a different count other than the population count is used for a denominator (within the table) to calculate percentages, there should be a row in the table that identifies that number "n".
- Alternatively, a footnote should be included in each table with percentages to indicate the denominator for percentages.

Missing values

- A "0" should be used to indicate a zero frequency.
- A blank will be used to indicate missing data in an end-of-text table or subject listing.

Document: \\ieedc-nas01a:\Boehringer_Ingelheim\BI_695501\XXA39605\Biostatistics\Documentation\SAP\15
-v2.0\BI 1297.12 SAP v2.0 31JAN2018.docx

Author: Version Number: 2.0
Version Date: 31JAN2018

Template No: CS_TP_BS016 Revision 4
Effective Date: 01Apr2016

Reference: CS_WI_BS005

FIGURE OUTPUT CONVENTIONS

- Figures will be provided in PDF files using the SAS Output Delivery System (ODS) as generated by SAS.
- The image should be clear and of high quality when viewed in the Word document, and when printed.
- In general, boxes around the figures should be used.

FOOTNOTE INFORMATION

Footers should be defined as follows:

- A continuous line of underscores ('_') will follow the body of the table or listing prior to any footnotes at the bottom of the page
- Table footnotes should be defined using compute statements in the proc report, and should appear directly after the body of the table
- The program path and name and version number (if applicable) should appear as footnote 1 at the bottom of the page
- The date/time stamp should appear as footnote 2 at the bottom of the page
- Footnotes should be left-aligned.
- Footnotes should be in sentence case.
- Only "typewriter" symbols are permitted – e.g., "*", "\$", "#", "@", "&" and "+".
- The choice of footnote symbols should be consistent. E.g., if you have the footnote "# indicates last observation carried forward" for one table, the same symbol and footnote should indicate LOCF for all tables.
- If text wraps across more than one line (for a note), the first letter for all lines of text after the first one will be indented to align beneath the first letter of the text in the first line.
- The page identification in the format Page X of Y (where Y is the total number of pages for the output) should appear in the footer, right aligned.

Ordering of footnotes should be as follows:

- 1.) Source data listing reference, if necessary
- 2.) Abbreviations and definitions
- 3.) Formulae
- 4.) P-value significance footnote
- 5.) Symbols
- 6.) Specific notes

- Common notes from table to table should appear in the same order.

The symbols should appear in the same order as what they are defined in the table or listing, from left to right.

Document: \\ieedc-nas01a:\Boehringer_Ingelheim\BI_695501\XXA39605\Biostatistics\Documentation\SAP\15
-v2.0\BI 1297.12 SAP v2.0 31JAN2018.docx

Author: Version Number: 2.0
Version Date: 31JAN2018

Template No: CS_TP_BS016 Revision 4
Effective Date: 01Apr2016

Reference: CS_WI_BS005

Statistical Analysis Plan
Dates & Times

Depending on data available, dates and times will take the form yyyy-mm-ddThh:mm:ss.

Spelling Format

English US.

Presentation of Treatment Groups

For outputs, treatment groups will be represented as follows and in that order:

Treatment Group	For Tables and Graphs
BI 695501	BI 695501
US-licensed Humira®	Humira

Presentation of Visits

For outputs, visits will be represented as follows and in that order:

Long Name (default)	Short Name	Visits as per protocol
Day -28 to -1	D-28 to -1	
Day 1	D1	Baseline
Day 8	D8	Day 8 (Week 1)
...
Day 232	D232	...

Listings

All listings will be ordered by the following (unless otherwise indicated in the template):

- randomized treatment group (or treatment received if it's a safety output)
- center-subject ID
- date including Study Day (where applicable),
- For listings where non-randomized subjects are included, these will appear in a category after the randomized treatment groups labeled 'Not Randomized'.

The visit as recorded in the eCRF will be displayed in the listings (and not the remapped visit).

Document: \\eedc-nas01a:\Boehringer_Ingelheim\BI_695501\XXA39605\Biostatistics\Documentation\SAP\15-v2.0\BI 1297.12 SAP v2.0 31JAN2018.docx

Author: Version Number: 2.0
Version Date: 31JAN2018

Template No: CS_TP_BS016 Revision 4
Effective Date: 01Apr2016

Reference: CS_WI_BS005

